### 1.3. Neutralizing Antibodies Targeting SARS-CoV-2

SARS-CoV-2 infection induces a humoral immune response of varying magnitude. Total and neutralizing antibody titers in serum depend on several factors, including disease severity. Whether the development of neutralizing antibodies contributes to protection from re-infection and whether neutralizing antibodies are a correlate of protection in vaccinated individuals are subjects of intensive research efforts that include investigations on the longevity of the immune response.

SARS-CoV-2-neutralizing monoclonal antibodies have been isolated from phage display libraries, immunized animals, survivors of infection with the related betacoronavirus SARS-CoV, as well as from SARS-CoV-2-infected individuals. Most of the identified neutralizing antibodies interfere with viral infection by targeting the RBD of the spike protein that interacts with the host cell receptor ACE2. However, neutralizing antibodies targeting other epitopes on the SARS-CoV-2 S protein have also been characterized. When tested *in vitro* against authentic replication-competent SARS-CoV-2 or replication-deficient viruses pseudotyped with the SARS-CoV-2 spike protein, neutralizing antibodies can efficiently block or reduce viral infection, although the neutralizing potency between different neutralizing antibodies varies considerably. In addition, the development of antibody escape mutations during viral passage *in vitro* suggests that combinations of antibodies targeting different epitopes may be beneficial.

Indicating their potential for use in prevention of SARS-CoV-2 infection, administration of neutralizing monoclonal antibodies prior to SARS-CoV-2 challenge resulted in reduced clinical disease, reduced viral concentrations, and/or reduced pulmonary pathological findings across diverse animal models. For example, a serum concentration of 22 µg/ml of the human neutralizing antibody CC12.1 at the time of intranasal viral challenge resulted in protection from disease in a Syrian hamster model of SARS-CoV-2 infection. Taking the neutralizing potency of the administered human antibody CC12.1 against SARS-CoV-2 into account, a serum antibody concentration of 1.160-fold the pseudovirus IC50 was considered fully protective in this study. Similarly, administration of human SARS-CoV-2-neutralizing antibodies prior to respiratory SARS-CoV-2 challenge resulted in reduced viral replication and reduced pathological findings in lung biopsies in non-human primate models of SARS-CoV-2 infection.

When administered in a therapeutic setting several hours after viral challenge, human SARS-CoV-2-neutralizing monoclonal antibodies resulted in reduced viral titers in transgenic mouse models expressing human ACE2. In addition, antibody treatment 24 h and 72 h after viral challenge was associated with an expedited decline of viral RNA in respiratory swabs and reduced pathological signs of pulmonary inflammation in rhesus macaques.

These positive pre-clinical findings of potent human SARS-CoV-2-neutralizing antibodies have prompted the initiation of phase I to phase III clinical trials of different antibody candidates. In addition to establishing the safety and tolerability of neutralizing antibodies, these studies aim to evaluate antibody efficacy both in the therapeutic and preventive settings. For example, the SARS-CoV-2-neutralizing antibody LY-CoV555 has been investigated in recently SARS-CoV-2-infected outpatients with mild-to-moderate infection. A single intravenous infusion of a dose of 700 to 7,000 mg was overall well tolerated. While the effects on the decline of viral shedding were limited, a lower fraction of antibody-recipients reported COVID-19-related hospitalizations or emergency room visits compared to placebo recipients. Interim results of trials investigating combinations of SARS-CoV-2 neutralizing antibodies to SARS-CoV-2-infected ambulatory trial participants have also suggested beneficial antibody-mediated effects, including reduced viral shedding and improved clinical outcomes (e.g., reduced symptom duration, reduced rate of COVID-19-associated medical contacts). Based on these results, emergency use authorizations for the first monoclonal antibodies were recently granted by the FDA in SARS-CoV2-infected outpatients at high risk of disease progression or hospitalization.

#### **1.4. Application of Antibodies and Antibody-Derived Fragments by Inhalation**

Intravenous antibody application results in limited antibody concentrations in the epithelial lining fluid (ELF) of the lung. In addition, achieving peak antibody ELF concentrations can be considerably delayed (up to multiple days) after intravenous infusion of an antibody.

To provide an immediate onset of action with high local concentrations, application of antibodies and antibody-derived fragments has been investigated for different indications in clinical trials. For example, inhalation of the humanized monoclonal antibody omalizumab (E25) was investigated in a total of 22 trial participants with mild allergic asthma. In this trial, participants self-administered a solution containing 1 mg or 10 mg of omalizumab twice daily over a total treatment period of 8 weeks, using a PARI IS-2 nebulizer. Although no therapeutic effects as indicated by an attenuation of early phase responses to inhaled allergens were observed, the inhaled administration of omalizumab at both dose levels was considered to be well tolerated. Inhalation of full-length antibodies was also studied in a case series of three immunodeficient infants (2, 4, and 5 years) suffering from frequent upper respiratory tract infections (URTI). In an attempt to reduce the number of URTIs, a 4 mL dose of a 5% human polyclonal immunoglobulin solution (i.e., a 200 mg human IgG dose) was administered twice daily by inhalation for a period of >9 months. To this end, an aerosol was generated using the eFLOW nebulizer (PARI GmbH) and applied using a children's facemask. During the

treatment period, a reduced number of URTIs was observed. Importantly, no adverse events related to the inhalation of aerosolized full-length IgGs were reported despite a daily administration of 400 mg IgG a day for multiple months.

Moreover, inhalation of antibody-derived fragments was also investigated for viral respiratory infection. In an ascending-dose healthy volunteer trial of the trivalent respiratory syncytial virus-targeting nanobody ALX-0171, doses of aerosolized ALX-0171 ranging from 2.1 mg to 210 mg were well tolerated, including a twice-daily dose of 105 mg administered for 5 days. In a phase 2b trial of ALX-0171 in children hospitalized with lower respiratory tract RSV infection, nebulized ALX-0171 at doses up to 9 mg/kg was not considered to be related to any serious adverse event. Thus, inhaled administration of antibody-derived molecules appeared generally safe in the presence of a lower respiratory tract viral infection.

### 1.5. DZIF-10c

DZIF-10c is a potent human SARS-CoV-2-neutralizing antibody that was identified from a blood sample of a COVID-19-convalescent patient obtained 35 days after diagnosis of infection. To isolate SARS-CoV-2-neutralizing antibodies from this and 11 additional patients, single memory B cells reactive to the SARS-CoV-2 spike protein were sorted using flow cytometry. Antibody heavy and light chain sequences were subsequently amplified from individually lysed cells using specific reverse transcription polymerase chain reaction (RT-PCR) and sequenced, facilitating the recombinant production of exact antibody replicates. Using this approach, the human monoclonal antibody HbnC3t1p1\_F4 was identified and later modified by eliminating the heavy chain C-terminal lysine to reduce potential charge heterogeneity, resulting in antibody DZIF-10c. DZIF-10c is a monoclonal antibody of the IgG1 kappa isotype with low somatic hypermutation compared to its germline sequence (% germline nucleotide identity of 93.2% and 96.1% for the heavy chain and light chain variable genes, respectively).

DZIF-10c targets the receptor binding domain (RBD) of the SARS-CoV-2 spike protein with high affinity. When tested *in vitro*, DZIF-10c demonstrates potent neutralizing activity both against authentic SARS-CoV-2 as well as SARS-CoV-2 spike-typed pseudoviruses. For example, infection of Vero E6 cells with the SARS-CoV-2 variant BavPat1/2020 was completely blocked in the presence of DZIF-10c at concentrations as low as 0.05 µg/ml as indicated by the absence of detectable cytopathic effects. Moreover, DZIF-10c demonstrated high activity against a panel of six SARS-CoV-2 pseudovirus variants with an average 50% inhibitory concentration (IC50) of 0.007 µg/ml in a neutralization assay using ACE2-expressing human 293T cells.

DZIF-10c has also been studied in animal models of SARS-CoV-2-infection. Mice expressing human ACE2 after transtracheal transduction by a recombinant adenovirus encoding for ACE2 [REDACTED] can be challenged with SARS-CoV-2, resulting in viral replication in pulmonary tissues. To investigate its therapeutic activity, DZIF-10c was administered [REDACTED] after SARS-CoV-2 challenge either by intraperitoneal injection or intranasal instillation. While high titers of infectious virus could be detected in lung tissues of animals treated with isotype control antibodies, [REDACTED] [REDACTED] undetectable levels of infectious SARS-CoV-2 (ACE2-transduced mice) were observed after DZIF-10c treatment.

Thus, DZIF-10c is a highly potent human SARS-CoV-2-neutralizing monoclonal antibody with promising potential for use in the treatment and prevention of SARS-CoV-2 infection.

## **2. Objectives of the Clinical Trial**

### **2.1. Rationale for the Clinical Trial**

This clinical trial is the first-in-human study for the inhaled application of the SARS-CoV-2-neutralizing human monoclonal antibody DZIF-10c. It is intended to investigate the safety and tolerability of DZIF-10c by inhalation, including by combined administration by inhalation and intravenous infusion, in humans and to support the further development of DZIF-10c for treatment and prevention of SARS-CoV-2 infection.

### **2.2. Primary Objective**

- To evaluate the safety and tolerability of a single inhaled application of DZIF-10c in SARS-CoV-2-uninfected and SARS-CoV-2-infected individuals.
- To evaluate the safety and tolerability of a single combined inhaled and intravenous application of DZIF-10c in SARS-CoV-2-infected individuals.

### **2.3. Secondary Objectives**

All to be determined after a single inhaled application of DZIF-10c or a single combined inhaled and intravenous application of DZIF-10c:

- To determine the systemic DZIF-10c exposure ( $AUC_{0-672h}$  (i.e., from the day 0 to the day 28 visit)).
- To determine the development of antibodies targeting DZIF-10c (anti-drug antibodies, ADA).
- To determine the effect of DZIF-10c on SARS-CoV-2 shedding in nasopharyngeal swabs by qRT-PCR.

### **2.4. Exploratory Objectives**

All to be determined after a single inhaled application of DZIF-10c or a single combined inhaled and intravenous application of DZIF-10c:

- To evaluate the effect of DZIF-10c on viral shedding in nasopharyngeal swabs determined by the presence of infectious virions in SARS-CoV-2-infected individuals.
- To evaluate the effect of DZIF-10c on viral shedding in oropharyngeal swabs determined by qRT-PCR in SARS-CoV-2-infected individuals.
- To evaluate the effect of DZIF-10c on viral shedding in oropharyngeal swabs determined by the presence of infectious virions in SARS-CoV-2-infected individuals.

- To evaluate the frequency of COVID-19-related hospitalization or medical contacts after DZIF-10c application in SARS-CoV-2-infected individuals.
- To evaluate the effect of DZIF-10c administration on symptom resolution in SARS-CoV-2-infected individuals symptomatic at baseline.
- To evaluate the effects of DZIF-10c administration on the viral sequence and the development of viral escape mutation that might arise.
- To evaluate SARS-CoV-2-specific immune responses following DZIF-10c application.
- To evaluate the effect of DZIF-10c application on viral replication in respiratory samples as determined by subgenomic mRNA levels in SARS-CoV-2-infected individuals.
- To determine the further pharmacokinetic profile of DZIF-10c.

##### Represented by

#### 3.2. Coordinating Investigator

#### 3.3. Statistician

### 3.4. Safety Monitoring Committee

A Safety Monitoring Committee (SMC) will be established to provide assessments of the participants' safety during the conduct of the clinical trial and to provide recommendations on dose escalation. This SMC will also oversee the safety of participants in a parallel clinical trial on the intravenous infusion of DZIF-10c (Uni-Koeln-4288, EudraCT: 2020-003503-34). The SMC will review data from both trials as they progress to ensure consistent and complete overview of DIF-10c safety data independent of the route of administration. Details will be provided in the SMC charter.

The SMC will be composed of three independent individuals with no connection to the Sponsor, who are not involved in the conduct of the clinical trial beyond their role in the SMC, and who do not have any direct responsibility for the clinical care of the study participants outside of the clinical trial. In addition, a Pharmacovigilance designee of Boehringer Ingelheim may be assigned as standing member of the SMC without voting right. Principal Investigators (PIs), designees of the Sponsor or Boehringer Ingelheim, and/or designees of the Monitor may be invited by the SMC for participation in SMC meetings to provide information on the conduct of the clinical trial and to answer questions by the SMC.

Meetings of the SMC will be conducted through video conference, by phone, or in-person as deemed necessary by the SMC. If scheduling problems prevent a timely meeting, review and comment may alternatively be conducted by E-Mail. One member will be appointed chair of the SMC and be responsible for summarizing SMC meetings and informing the Coordinating Investigator and Sponsor about meetings and recommendations in writing. The SMC chair may select another SMC member as designee to perform these tasks. A quorum for SMC meetings will require the participation of at least two SMC members with voting rights.

Ad-hoc SMC meetings will be conducted prior to enrolment into **Groups 1B, 1C, 2B, 2C, and 2D** to provide recommendations on proceeding with the dose escalation scheme. A review of the safety data from the intravenous doses administered in the Uni-Koeln-4288 trial will be conducted prior to inclusion of the intravenous dose in **Group 2D** to decide on whether to include intravenous infusion of DZIF-10c and at which dose. A lower dose than the targeted 40 mg/kg dose will be used in case that a lower maximum tolerated dose for the intravenous infusion of DZIF-10c has been determined in the trial Uni-Koeln-4288.

Additional SMC meetings may be scheduled on an as-needed-basis if deemed necessary by the members of the SMC, the Sponsor, or the Principal Investigators.

On an interim basis, the SMC will also be asked to review the following data:

- Any grade 3 or higher Adverse Events (AEs) that are deemed to be related to DZIF-10c by the Investigators.
  - These events will also be assessed as potential late-occurring dose-limiting toxicities (i.e., after dose-escalation has proceeded and/or been completed) to evaluate whether a change to study dosing is warranted.
  - In case of grade 3 or higher AEs deemed related to DZIF-10c occurring in two or more participants, administration of DZIF-10c will be halted until a SMC review has been completed to provide recommendations regarding subsequent study enrolment.
- Serious Adverse Events (SAEs) that are deemed related to DZIF-10c by the Principal Investigator or designee. Such events need to be reported to the SMC within one business day of the Sponsor becoming aware of the event.
  - No additional administration of DZIF-10c will occur after an SAE deemed related to DZIF-10c until an SMC review has been completed to provide recommendations regarding subsequent study enrolment.
  - In case of life-threatening, fatal, or permanently disabling SAEs deemed related to DZIF-10c, no further administration of DZIF-10c will occur until a consensus plan has been approved by the SMC, Investigators, the Sponsor, the principal ethics committee, and the PEI.

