### **9.1.6. Dose-Limiting Toxicities**

A dose-limiting toxicity (DLT) will be defined as any grade 3 or higher adverse event during the dose escalation phase of the trial (**Groups 1A-1C, 2A-2C**) that is assessed by the trial investigators to be related to DZIF-10c. For details on reporting requirements see section 9.3.1.

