#### **9.3.1. SAE, AESI and DLT Reporting**

All serious adverse events (SAEs) occurring between the provision of informed consent to participant in the trial and the participant's last trial visit must be reported by the local trial investigator to the sponsor without delay and at the latest within 24 hours of becoming aware of the SAE.

To this end, the provided SAE report forms must be completed and submitted by fax or E-Mail to the Clinical Trials Center Cologne (CTCC, ZKS Köln) to which the sponsor has delegated the SAE management procedures:

**SAE Dedicated Facsimile:** [REDACTED]

**SAE Reporting E-Mail:** [REDACTED]

Similarly, AESIs should be reported on AESI report forms and must be completed and submitted by fax or E-Mail to the Clinical Trials Center Cologne (CTCC, ZKS Köln) within 24 h of the site becoming aware of the event.

Finally, DLTs occurring during the dose-escalation phase of the trial (**Groups 1A-1C, Groups 2A-2C**) must be reported by submitting the AE/DLT report form by fax or E-Mail to the Clinical Trials Center Cologne (CTCC, ZKS Köln) within 24 h of the site becoming aware of the event.

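### In Group 2D, non-serious, non-AESI related grade 3 or higher events have no stated reporting deadline, although two such participants trigger a mandatory halt

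*Protocol*

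**What the plan says.** Protocol section 3.4 lists what the SMC reviews on an interim basis. The bullet on related grade 3 or higher adverse events contains the rule: "In case of grade 3 or higher AEs deemed related to DZIF-10c occurring in two or more participants, administration of DZIF-10c will be halted" until the SMC has reviewed the events. The same bullet asks the SMC to consider such events as possible late DLTs, including those arising "after dose-escalation has proceeded and/or been completed".

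The next bullet deals with related SAEs. There a single event is enough: "No additional administration of DZIF-10c will occur after an SAE deemed related to DZIF-10c until an SMC review has been completed". It also carries a clock: "Such events need to be reported to the SMC within one business day of the Sponsor becoming aware of the event". The grade 3 or higher bullet has no such clock.

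Reporting by sites is set out in sections 9.3 and 9.3.1. SAEs "must be reported by the local trial investigator to the sponsor without delay and at the latest within 24 hours" of awareness. AESIs and DLTs have the same 24-hour limit, and pregnancy has its own in section 9.3.2. The DLT item begins "Finally, DLTs occurring during the dose-escalation phase of the trial" and lists Groups 1A-1C and 2A-2C. Section 9.1.6 defines a DLT as "any grade 3 or higher adverse event during the dose escalation phase of the trial", names the same groups and requires relatedness; section 5.2.1 agrees. All other adverse events are documented in the case report form (section 9.2.1) and become expedited only if they turn serious. Section 6.2.1 describes online data entry but gives no entry deadline.

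**The concern.** The halt depends on someone knowing, soon after it happens, that a second participant has had a qualifying event. In Group 2D one class of qualifying event has no stated route by which that knowledge arrives promptly. Section 3.6 foresees up to seven sites, so a site that sees its first such event cannot know whether another site has already had one.

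What is at stake is the pause itself. Group 2D receives the highest tested and tolerated inhaled dose, and one arm receives the first combined inhaled and intravenous administration. The limit of one participant per dose per day in section 4.1.1 applies only to escalation, and section 5.5 allows Group 2D to be treated as outpatients. If the second event is noticed late, further participants could be dosed in the interval.

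**Working it through.** The plan gives no figure for this point, so the main check sets the sections side by side. The arithmetic at the end is illustration.

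1. **Does the halt cover Group 2D?** Yes. The rule in 3.4 names no phase or group, and its companion item expressly covers events after escalation is complete.

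2. **Which channel carries a related grade 3 or higher event in Group 2D?**

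| Type of event | Site to sponsor | Sponsor to SMC |
|---|---|---|
| Serious | 24 hours (9.3.1) | one business day (3.4) |
| Non-serious, AESI up to the day 7 visit | 24 hours (9.3, 9.3.1) | none stated |
| Non-serious, not an AESI | none stated | none stated |

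   The last row includes clinically significant laboratory abnormalities, which section 5.2.1 has graded and reported as adverse events; Appendix II B schedules safety laboratory tests to day 90. It also includes non-serious events after day 7, because AESIs are documented as such only to the day 7 visit (sections 5.2.1 and 8.1.3).

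3. **What does the two-participant rule add?** One related SAE already stops dosing. The two-participant rule therefore adds protection mainly for non-serious events. AESIs aside, those are the events in the last row.

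4. **Who keeps the count?** No section names a role that adds up events across sites. Read literally, the count also spans phases: section 4.1.1 lets escalation proceed after one DLT in a group, so one later event in Group 2D could complete the trigger.

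5. **Is there a backstop in the SAP?** Not in time. Interim analysis 2 (SAP 9.1.2) tabulates DLTs for phase IIa, but only after the last randomised participant has 7 days of follow-up, when dosing is finished.

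6. **Illustration of size.** Inputs from the protocol: 60 participants in Group 2D (8.2), randomised 1:1:1 (4.1), so 2/3 (40) receive DZIF-10c. Assumptions: enrolment over 91 days (all of Q2 2021, the tentative quarter for the last first visit) or, faster, 45 days; and the lag from trigger to detection.

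   Further DZIF-10c dosings = (60 / enrolment days) x lag in days x 2/3.

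| Enrolment | 1-day lag | 7 days | 14 days | 28 days |
|---|---|---|---|---|
| 91 days (0.66 per day) | 0.4 | 3.1 | 6.2 | 12.3 |
| 45 days (1.33 per day) | 0.9 | 6.2 | 12.4 | 24.9 |

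   These figures assume that the trigger has been met and that enough participants remain to be enrolled.

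7. **How likely is the trigger?** With p the assumed proportion of DZIF-10c recipients who have a related, non-serious, non-AESI grade 3 or higher event, P(at least 2 of 40) = 1 - (1-p)^40 - 40p(1-p)^39. This gives 6.1% at p = 1%, 19.0% at 2%, 60.1% at 5% and 92.0% at 10%. The documents give no value for p.

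**The case against.** The gap is narrow. SAE and AESI reporting within 24 hours applies in Group 2D. Many grade 3 events will be serious, since the grading in section 9.2.2 includes events for which hospitalisation is indicated, and section 9.1.3 lets an investigator classify any medically important event as serious. This stands, although that last route is discretionary. A reader might infer that the halt has no timely information at all in Group 2D; the documents do not support that.

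A reader might also infer that dosing would continue past the trigger. The protocol defers to an SMC charter (3.4), an Investigator Handout on reporting (9.3), and a data management plan and eCRF completion requirements (6.2.1). None was available, and any could set a deadline. The Clinical Trials Center Cologne holds data management, monitoring and safety management together (3.5) and checks data as they are entered online. So only *could continue* is justified. Even so, the protocol itself lists the expedited categories and leaves this one out, and a mandatory halt should not rest on documents outside it.

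Finally, it is tempting to add that a related grade 3 event at day 56 in Group 2A falls outside expedited reporting once escalation has ended. Sections 5.2.1, 9.1.6 and 9.3.1 identify the phase by its groups and set no day limit, so that event can be read as a reportable DLT. The wording is ambiguous, and the Group 2D gap does not depend on it.

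**Conclusion.** The point holds for one defined class: related grade 3 or higher events in Group 2D that are neither serious nor AESIs. For these, sections 9.3 and 9.3.1 do not supply what the halt in 3.4 needs: a transmission deadline, an SMC notification deadline and a named keeper of the count.

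Its size cannot be derived from the documents. The 6 to 12 further DZIF-10c dosings (91-day enrolment, 14- to 28-day lag), against about 0.4 with a one-day lag, rest on assumed accrual and lag and are conditional on the trigger being met, the probability of which is itself unknown. They should not be read as a forecast. Given the narrow class and the unseen supporting documents, this is a cheap improvement rather than a condition for proceeding.

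**What to change.** Reconcile section 3.4 with sections 9.3 and 9.3.1:

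- Extend the existing expedited AE/DLT report to every related grade 3 or higher adverse event in Group 2D, and clarify that it covers late events in Groups 1A-1C and 2A-2C.
- State a sponsor-to-SMC notification deadline under the grade 3 or higher bullet in 3.4.
- Name the role that keeps the count across sites, and say whether it runs across both phases.

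If the SMC charter or Investigator Handout already contains these provisions, a cross-reference in 3.4 and 9.3.1 is enough. The halt threshold and clinical management are untouched. The cost is a few sentences, wider use of a form that already exists, and probably a few extra expedited reports.
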